### **8.3.6.2 Efficacy assessment**

SIJ and spine PET-CT and PET-MRI scans will be independently assessed at each time point (Baseline, Week 12 and Week 48) in a blinded fashion by two reviewers, with an additional adjudication read by a third reviewer, if applicable. Independent reviewers will assess PET-MRI/PET-CT examinations quantitatively using VU University Medical Center (VUMC)'s in-house software (ACCURATE).

Initially, two primary readers will independently assess the images visually to identify PET-positive lesions in the SIJ and spine. The readers will dichotomously score the presence or absence (1 versus 0) of PET-positive lesions in each side of the SIJ (Left and Right) and at each of the 24 spinal levels and 4 spinal regional levels [C2-C7 (Cervical), T1-T12 (Thoracic), L1-L5 (Lumbar), Sacrum] in each of the following 8 spinal locations:

- Process spinosus
- Costo-vertebral (right)
- Costo-vertebral (left)
- Facet joint (right)
- Facet joint (left)
- Anterior vertebra
- Posterior vertebra
- Vertebra (other)

For each subject, PET-positive lesions may be identified in one or both sides of the SIJ and in one or more of the 192 possible anatomical locations (spinal location/level combinations). It is expected that only one lesion for a subject may be separated/identified in each side of the SIJ or individual anatomical location in the spine, therefore, there is a direct mapping of a subject's lesion to a SIJ side or spinal location/level.

If there is a discrepancy between the two primary readers in the presence of PET-positive lesion assessment (Yes versus No for lesions in any side of the SIJ and 1 versus 0 for lesions in any spinal location), a consensus adjudication will take place with a third reader who will also be blinded to the clinical data. This reader will make an independent assessment and the results of the adjudication will be considered as the final assessment of the presence of PET-positive lesions.

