Another reader who has not been involved in the visual identification of the PET-positive lesions, either as a primary reader or an adjudicator, will then draw volumes of interest (VOIs) on the pre-identified PET-positive lesions. In the case that no PET-positive lesions have been identified for a subject, then the final review step to draw VOIs will not occur. Efficacy PET-MRI/PET-CT review will occur provided that an acceptable PET-CT or PET-MRI scan is available and that PET-positive lesions were identified on the previous scan (for the Week 12 and Week 48 visits). During the PET-positive lesion VOI review, the independent reviewer will perform a quantitative assessment in ACCURATE and record the standard uptake values of  $^{18}\text{F}$ -fluoride in VOIs, corrected for both body weight and individual integrated whole blood activity concentration (SUVauc) for each PET-positive lesion identified during the PET-positive lesion identification review.

Data from the visual identification of PET-positive lesions and the results of the quantitative VOI review (i.e. SUVauc) will be listed, for each independent reader and adjudicator (if applicable), for each anatomical location in the spine, and for each side of the SIJ, by treatment group and visit for subjects in the SS who were enrolled into the PET-MRI/PET-CT substudy.

No formal statistical modelling of the PET-MRI/PET-CT imaging data will be performed for this substudy; only summaries will be presented together with 95% CIs for mean values, as applicable.

The summaries described below based on the visual identification of PET-positive lesions will include the final assessment data, ie, if adjudication was performed, then the adjudicated data will be summarized, otherwise data from one of the primary reviewers will be summarized.

All summaries will be presented for the PET-PPS.

Since the attenuation correction and quantification is variable in PET-MRI scans, PET-MRI imaging data will be listed but will not be aggregated with the PET-CT imaging data in the summaries.

Due to the predicted sparseness of the number of PET-positive lesions in each of the individual anatomical locations of the spine, data will be pooled as follows for the purpose of some of the summaries:

- In the SIJ and spine overall (across the SIJ and all anatomical locations in the spine);
- In the SIJ overall (across both sides), and split by Left and Right side;

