Observed  $SUV_{auc}$  values for each lesion will be pooled across subjects and summarized by visit for each of the pooled locations, as described above. In the spine, the observed  $SUV_{auc}$  values will only be summarized for the anatomical locations in which at least 1 PET-positive lesion is identified. Descriptive statistics will be presented including 95% CIs for the mean observed  $SUV_{auc}$  values. In addition, changes and percentage changes in  $SUV_{auc}$  values between visits will be calculated for each subject's PET-positive lesion in the SIJ and spine, i.e. Week 12 - Baseline, Week 48 - Baseline and Week 48 - Week 12. These changes in  $SUV_{auc}$  values will be pooled across subjects and summarized by visit for each of the pooled locations described above. Descriptive statistics will be presented including 95% CIs for mean changes and percentage changes in  $SUV_{auc}$  values between visits.

Spaghetti plots of observed  $SUV_{auc}$  values for lesions in the SIJ and spine will be presented over time for the SIJ overall, the spine overall, and for each spinal regional level (Cervical, Thoracic, Lumbar, Sacrum) by treatment group.

In addition, percentage changes in  $SUV_{auc}$  values for lesions in the SIJ and spine will be summarized using waterfall plots. These plots will identify subjects' lesions by treatment group and will be presented by pooled location (as described above, as applicable) and for each visit comparison (Week 12 – Baseline, Week 48 – Baseline and Week 48 – Week 12).

The maximum of a subject's observed  $SUV_{auc}$  values will be calculated across the pooled locations described above. This maximum  $SUV_{auc}$  value per subject will be summarized at each visit together with changes and percentage changes from Baseline between visits. Descriptive statistics will be presented including 95% CIs for the mean and the mean changes/percentage changes in the maximum  $SUV_{auc}$  values.

The mean and 95% CI for the maximum  $SUV_{auc}$  values per subject in the SIJ and spine over scheduled time will also be presented by treatment group. The same plot will be repeated for the changes and percentage changes in the maximum  $SUV_{auc}$  value per subject with treatment group overlaid on the same plot.

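### The lesion-level SUVauc summaries give 95% CIs that ignore several lesions coming from one subject, so they are too narrow in the pooled rows

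*SAP*

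**What the plan says.** SAP 2.2.1.3 declares the bone-formation variable in two parts: SUVauc for each PET-positive lesion, and the maximum SUVauc over a subject's lesions in the spine and SIJ.

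SAP 8.3.6.2 describes the summaries:

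- Observed lesion values are pooled over subjects by visit and location, with 95% CIs for the means. Lesion-level changes and percentage changes "will be pooled across subjects and summarized by visit for each of the pooled locations described above". For these, "Descriptive statistics will be presented including 95% CIs for mean changes and percentage changes in" SUVauc.
- The pooled locations are SIJ and spine together, SIJ overall and by side, spine overall, the four spinal regions and, depending on how the lesions are distributed, individual levels and locations.
- A subject may have lesions on both SIJ sides and at any of 192 spinal sites. At the finest grain, "It is expected that only one lesion for a subject may be separated/identified in each side of the SIJ or individual anatomical location".
- "No formal statistical modelling of the PET-MRI/PET-CT imaging data will be performed for this substudy"; only summaries are planned, with CIs for means as applicable.
- The per-subject maximum has its own summary, with "95% CIs for the mean and the mean changes/percentage changes in the maximum" SUVauc.

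Modelling that accounts for several lesions per subject appears once, at the end of the section. It is optional and concerns other questions: the link with ASDAS, and ASAS20 responders against non-responders. SAP 3.1 says that CIs for means appear where stated, and gives no rule for clustered data.

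**The concern.** Lesions in one subject share that subject's disease activity, treatment response and scanner. Some positive correlation is therefore likely, though the documents do not report one. An ordinary CI over lesions divides the spread by the square root of the number of lesions, as if each were an independent observation. When subjects contribute several lesions, the independent information is closer to the number of subjects, and the interval overstates how well the arm mean is known.

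At stake is how the substudy is read. SAP 2.4 raises the total sample to at least 72 so that at least 25 evaluable PET subjects are included, and expects them to characterize broad differences between treatment groups. With so few subjects per arm, readers will probably judge the arms by whether these intervals overlap.

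**Working it through.** **Inputs from the documents**

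- Unit of pooling: the lesion; interval: 95% CI for the mean (SAP 8.3.6.2).
- Possible lesions per subject: 2 SIJ sides, plus (6 + 12 + 5 + 1) = 24 spinal levels × 8 locations = 192 spinal sites.
- Substudy size: at least 25; randomization 2:1 (SAP 2.4).
- PET-MRI data are not aggregated with PET-CT data in the summaries (SAP 8.3.6.2), so a table may hold fewer than 25 subjects.

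**Assumptions**

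- The 2:1 ratio carries into the substudy: 25 × 2/3 ≈ 17 and 25 × 1/3 ≈ 8 subjects (k).
- Lesions per subject (m) and ICC are in neither document, so a range is shown.
- The CI is the ordinary t-interval over lesions. The SAP gives no formula; this is the default when only descriptive statistics are planned and modelling is excluded.

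The plan states no width or coverage for these summaries, so it has no figure to reproduce.

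**Large-sample formulas**

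Design effect DE = 1 + (m − 1) × ICC. The CI should be √DE times as wide, and the coverage of the unadjusted interval is 2Φ(1.96/√DE) − 1.

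- m = 2, ICC 0.1: DE = 1 + 1 × 0.1 = 1.10; √DE = 1.05; coverage 93.8%.
- m = 5, ICC 0.3: DE = 1 + 4 × 0.3 = 2.20; √DE = 1.48; coverage 81.4%.
- m = 10, ICC 0.5: DE = 1 + 9 × 0.5 = 5.50; √DE = 2.35; coverage 59.7%.

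**Simulation at the actual scale** (normal data, equal m, 20,000 data sets per cell)

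| m | ICC | Lesion CI, k = 8 | Lesion CI, k = 17 | Subject-mean CI, k = 8 / 17 |
|---|---|---|---|---|
| 1 | 0.1 | 94.7% | 95.1% | 94.7% / 95.1% |
| 2 | 0.1 | 94.2% | 93.9% | 95.1% / 95.2% |
| 5 | 0.3 | 81.0% | 81.7% | 95.1% / 95.2% |
| 10 | 0.5 | 58.5% | 59.5% | 94.9% / 95.1% |

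With one lesion per subject the two intervals are identical, which is why left SIJ, right SIJ, single-site rows and the per-subject maximum are not affected. Coverage hardly differs between 8 and 17 subjects, so recruiting more would not cure it.

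**Unequal counts** (1 to 10 lesions per subject, all equally likely; k = 8 / 17; 10,000 data sets)

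- Lesion CI: 88.1 / 87.8% (ICC 0.1), 75.8 / 76.2% (0.3), 65.7 / 67.6% (0.5).
- Lesion mean with a CR2 cluster-robust CI and Satterthwaite degrees of freedom: 95.1 / 94.9%, 94.2 / 94.8%, 94.8 / 94.8%.

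**Width, subject-based over lesion-based, k = 8** (ratio of mean widths): 1.195/1.043 = 1.15 (m = 2, ICC 0.1); 1.069/0.624 = 1.71 (m = 5, 0.3); 1.194/0.427 = 2.80 (m = 10, 0.5). These exceed √DE because the t quantile also changes. In the last case it is 2.365 on 7 degrees of freedom against 1.990 on 79, and 2.35 × 2.365/1.990 = 2.79.

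**The case against.** The best case against the point is that it hardly matters. Bone formation is exploratory, the PET outputs are descriptive, and no test, success rule or planned decision uses these intervals. The per-subject maximum, one of the two declared parts of the variable, already has CIs free of clustering, and the only SUVauc plots specified with CIs show that maximum. SAP 3.1 suppresses the CI when n is 3 or fewer, so the sparsest rows carry none. The SAP gives no CI formula, and the low figures need many lesions per subject, which nothing in the documents establishes.

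All of this limits the importance, and it stands. It does not make the intervals right. The maximum is a different quantity and says nothing about the precision of the per-lesion mean, which is declared alongside it. The small-n rule removes tiny rows; it does not address correlation in larger ones. The closing remark on modelling several lesions per subject shows that the authors knew of the structure, but it does not reach these CIs.

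A reader might also infer that the change summaries are biased because resolved lesions drop out. SUVauc is recorded "for each PET-positive lesion identified during the PET-positive lesion identification review", and "In the case that no PET-positive lesions have been identified for a subject, then the final review step to draw VOIs will not occur". The SAP does not say how a Baseline lesion that is later read negative is handled, so this is an inference. Putting a number on it would need a fixed SUVauc limit for positivity, whereas lesions are identified visually, with adjudication. The same section also plans summaries of the change in the number of lesions per subject, and bar charts of lesion counts by arm and visit, which would show net lesion loss. The documents do not support a claim of bias of any stated size.

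**Conclusion.** The point holds for rows that can contain more than one lesion per subject: SIJ plus spine, SIJ overall, spine overall, spinal regions, and levels or locations pooled over several sites. Under the default lesion-level interval, their 95% CIs are too narrow whenever the within-subject correlation is positive.

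The size cannot be fixed from the documents. It runs from negligible (two weakly correlated lesions) to serious (ten lesions at ICC 0.5), and the documents favor neither end.

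Impact is low. The primary conclusion is not touched. A reader might infer an inflated error rate for a comparison of the arms, but no between-arm test of SUVauc is planned. What is wrong is the precision shown for each arm's per-lesion mean.

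**What to change.** In SAP 8.3.6.2, for rows that can hold more than one lesion per subject:

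1. Keep the planned lesion mean and base its 95% CI on the subject, using a cluster-robust interval with small-sample correction (for example CR2 with Satterthwaite degrees of freedom). The estimate does not change.
2. Alternatively, use a t-interval on per-subject means. It is simpler and plainly not modelling, but it weights subjects equally, so the estimate can differ from the lesion mean.
3. Show the number of subjects beside the number of lesions. SAP 3.1 treats n as a count of subjects, while the abbreviation list treats it as a count of observations, so a single n would be ambiguous here.

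Name one method before unblinding. On lesion dropout, at most add a footnote that the SUVauc change summaries include only lesions with a recorded SUVauc at both visits.

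The cost is SAP wording and programming, with no new scans or reads. The intervals will be wider, by about 1.15 to 2.8 times with 8 subjects over the assumed range.

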## **9 PHARMACOKINETICS AND PHARMACODYNAMICS**

### **9.1 Pharmacokinetics**

There will be no calculation of PK parameters for this study. The analysis of PK data for this study will focus on the concentrations of CZP and BKZ only. Any additional PK analyses will be performed only if required.

The actual blood sampling times for BKZ and CZP concentrations will be obtained in days relative to the start time of the first administration of IMP for all sampling time points.

Individual blood sampling times and concentrations of BKZ and CZP will be listed by treatment group for the SS and will include the actual sampling time in days relative to the first.

Individual concentrations will be summarized at each scheduled time point based on the PK-PPS, using n, mean, median, SD, minimum, maximum, geometric mean and 95% CI, and geoCV (assuming log-normally distributed data).

Individual concentration versus time (day) profiles will be presented graphically on linear and semi-logarithmic scales with all subjects overlaid on the same plot (spaghetti plots). Geometric mean profiles, separately for BKZ and CZP, will also be presented on both linear and semi-logarithmic scales respectively with and without the corresponding lower and upper limit of the 95% CI. All semi-logarithmic plots will include the respective LLOQ marked on the y-axis.

The following rules will apply for PK data listings and summaries:

- Values below the LLOQ will be reported as BLQ in the listings
- Descriptive statistics of concentrations will be calculated if at most  $\frac{1}{3}$  of the individual data points are missing or are not quantifiable (<LLOQ). Values that are BLQ will be replaced by the numerical values of the LLOQ/2 in this instance. However, if  $n \leq 3$ , then only n, minimum and maximum will be presented (where 'n' refers to the number of quantifiable values). The other descriptive statistics will be left blank.
- The 95% CI for the geometric mean will be left blank if the SD is 0

The geoCV (%) will be calculated using the following formula where  $SD_L$  is the standard deviation from the log-transformed data:

$$geoCV (\%) = 100 \times \sqrt{\exp(SD_L^2) - 1}$$

## 9.2 Pharmacodynamics

All PD variables will be listed by treatment group, subject and visit including changes from Baseline, based on the SS.

Observed values and changes from Baseline will be summarized by treatment group and visit based on the PD-PPS.

Figures of mean and mean changes from Baseline over time will be presented with separate plots for each variable and both treatment groups overlaid on the same plot.

The rules for handling any values that are BLQ or ALQ are described in [Section 4.2.2](#).

## 10 IMMUNOLOGICAL ANALYSES

The results for the ADA measurements will be listed by treatment group and time point based on the SS, including the Screening assay, confirmatory assay and titre (if applicable).

A cut point will be determined by the bioanalytical laboratory that will be used to determine the status of ADA as above the cut point (ACP) or below the cut point (BCP). For any ADA levels that are ACP, a further confirmatory assay will be performed, the results of which will be determined as either 'confirmed positive' (CP) or 'not confirmed positive' (NCP). For samples that are CP, a further titre assay will be performed and the ADA titre will be reported. The following definitions will be applied:

- An ADA status for a given time point of positive will be concluded for any subject with an ADA level that is ACP and CP at any time point
- An ADA status of negative for a given time point will be concluded for any subject with an ADA level that is either BCP or ACP and NCP at any time points
- A subject will be classified as having ADA positivity at Baseline if the Visit 2 (Week 0), pre-dose result is ACP and CP
- A subject will be classified as having treatment-induced ADA positivity when meeting 1 of the following criteria:
  - The Baseline result is either BCP or ACP and NCP, and at least 1 post-Baseline time point is ACP and CP
  - The Baseline result is positive (ACP and CP) and at least 1 post-Baseline measurement shows a pre-defined fold increase in titre from the Baseline value (the fold increase from Baseline required to meet this criterion will be defined with the development of the assay and will be included in the TFLs)
- A subject will be classified as overall positive if at least 1 post-Baseline measurement is ACP and CP (this includes subject who have negative results at Baseline)
- A subject will be classified as overall negative if at all post-Baseline visits the ADA status is negative (this includes subjects who have positive [ACP and CP] results at Baseline)

The ADA status (positive/negative) will be summarized as a categorical endpoint (number and percentage of subjects) by treatment group, for all time points and overall, based on the PK-PPS. In addition, the first occurrence of treatment-induced ADA positivity (based on the definitions

above) will be summarized by treatment group (number and percentage of subjects) at each post-Baseline visit, based on the PK-PPS. This tabulation will count the number of subjects at each post-Baseline visit who fulfill at least 1 of the above defined criteria for treatment-induced positivity; subjects will be counted in the numerator based on the earliest visit at which 1 of these criteria is fulfilled. At other visits, subjects will be counted in the denominator (assuming a measurement is available). For all tabulations, percentages will be based on the number of observations at each visit.

Separate listings will be presented (based on the PK-PPS) showing the BKZ and CZP concentrations and ADA measurements in the same output in adjacent columns. The listing will include the BKZ and CZP concentration, ADA status (ACP or BCP) and confirmatory assay results if applicable (NCP or CP), together with the titre for results that are CP. In addition, the time since the previous administration of IMP will be reported (in days).

Finally, individual subject plots (based on the PK-PPS) will be presented displaying ADA titre, BKZ and CZP concentrations overlaid on the same figure using a semi-logarithmic scale.

The rules for handling values that are BLQ in the BKZ and CZP concentration data are described in [Section 4.2.4](#). For the ADA data, any negative results for which there are no titres available at a specific visit will be substituted with 0.001 for the purpose of the figure.

## 11 SAFETY ANALYSES

All analysis of safety variables will be performed using the SS.

### 11.1 Extent of exposure

All IMP administration details (including date and time of administration, body site and side of administration) will be listed. Additionally, the time between each dose will be listed.

The duration of exposure to BKZ (days) will be calculated separately for the Treatment Period and the Treatment Extension Period, where the last and first dose in each equation will be the last and first dose of IMP within the Treatment Period and Treatment Extension Period respectively:

$$\text{Exposure} = (\text{Date of Last Dose} - \text{Date of First Dose}) + 140 \text{ days}$$

The duration of exposure to CZP (days) will be calculated as follows:

$$\text{Exposure} = (\text{Date of Last Dose} - \text{Date of First Dose}) + 70 \text{ days}$$

The number of days added to the BKZ and CZP exposure calculations are 5 times the half-life of each drug, respectively: 5 x 28 days for BKZ and 5 x 14 days for CZP.

Missed doses will not be accounted for in the calculation above.

The number of injections received and duration of exposure will be listed for each subject and summarized by treatment group for the Treatment Period and Treatment Extension Period separately using descriptive statistics. This summary will be repeated for subjects in the SS who were randomized in the PET-MRI/CT substudy.

